3.6.3.3 Change from baseline

The time point for the mean change from baseline is defined as the latest time point at which $CR-T \ge 60\%$ and $CR-E \ge 80\%$, and week 17 was selected based on blinded data review prior to the database lock for any PRO analysis.

To assess the treatment effects on the PRO score change from baseline in the global health status/QoL, physical functioning, role functioning, FKSI-DRS score, and EQ-5D VAS, a constrained longitudinal data analysis (cLDA) model proposed by Liang and Zeger [11] will be applied, with the PRO score as the response variable, and treatment, time, the treatment by time interaction, and stratification factors used for randomization (See Section 6.3.2 of the protocol) as covariates.

The treatment difference in terms of least square (LS) mean change from baseline will be estimated from this model together with 95% CI. Model-based LS mean with 95% CI will be provided by treatment group for PRO scores at baseline and post-baseline time point.

The technical details on the cLDA model are in the appendix of this sSAP.

Line plots for the empirical mean change from baseline in EORTC QLQ-C30 global health status/QoL, physical functioning, role functioning, and FKSI-DRS score will be provided across all time points as a supportive analysis.

In addition, the model-based LS mean change from baseline to the specified post-baseline time point together with 95% CI will be plotted in bar charts for EORTC QLQ-C30 global health status/quality of life scores, all functioning, symptom scores, FKSI-DRS score, and EQ-5D VAS.

3.6.3.4 Time to Confirmed Deterioration (TTD)

The Kaplan-Meier method will be used to estimate the TTD curve for each treatment group. The estimate of median time to deterioration and its 95% confidence interval will be obtained from the Kaplan-Meier estimates. The treatment difference in TTD will be assessed by the stratified log-rank test, and two-sided nominal p-value will be reported. A stratified Cox proportional hazard model with Efron's method of tie handling and with a single treatment covariate will be used to assess the magnitude of the treatment difference (i.e, HR). The HR and its 95% CI will be reported. The same stratification factors used for randomization (See Section 6.3.2 of the protocol) will be used as the stratification factors in both the stratified log-rank test and the stratified Cox model.

The approach for the TTD analysis will be based on the assumption of non-informative censoring. The participants who do not have deterioration on the last date of evaluation will be censored. Table 7 provides censoring rule for TTD analysis.

Table 7 Censoring Rules for Time to Confirmed Deterioration

Scenario	Outcome				
Deterioration documented	Event observed at time of assessment (first deterioration)				
Ongoing or discontinued from study without deterioration	Right censored at time of last assessment				
No baseline assessments	Right censored at treatment start date				

3.6.3.5 Overall Improvement and Overall Improvement/Stability

Overall improvement rate will be analyzed, which is defined as the proportion of participants who have achieved an improvement as defined in Section 3.4.3 PRO Endpoints. Stratified Miettinen and Nurminen's method will be used for comparison of the overall improvement rate between the treatment groups. The difference in overall improvement rate and its 95% CI from the stratified Miettinen and Nurminen's method with strata weighting by sample size will be provided. The stratification factors used for randomization (See Section 6.3.2 of the protocol) will be applied to the analysis.

The point estimate of overall improvement rate will be provided by treatment group, together with 95% CI using exact binomial method by Clopper and Pearson (1934).

The same method will be used to analyze overall improvement/stability rate, which is defined as the proportion of participants who have achieved improvement/stability as defined in Section 3.4.3 PRO Endpoints.

Endpoint/Variable	Statistical Method	Analysis Population	Missing Data Approach
 Mean change from baseline in EORTC QLQ-C30 Global health status/QoL Physical functioning Role functioning FKSI-DRS And EQ-5D VAS 	cLDA model	FAS	Model-based.
 TTD in EORTC QLQ-C30 Global health status/QoL Physical functioning Role functioning And FKSI-DRS 	stratified log-rank test and HR estimation using stratified Cox model with Efron's tie handling method	FAS	Censored according to rules in Table 6.
Overall improvement and overall improvement/stability in EORTC QLQ-C30 • Global health status/QoL • Physical functioning • Role functioning And FKSI-DRS	Stratified Miettinen and Nurminen method	FAS	Participants with missing data are considered not achieving improvement/stability.
Abbreviations: cLDA = constra quality of life. TTD=time to c	6	·	

3.6.3.6 Analysis Strategy for Key PRO Endpoints

3.6.4 Demographic and Baseline Characteristics

The comparability of the treatment groups for each relevant demographic and baseline characteristic will be assessed by the use of tables and/or graphs. No statistical hypothesis tests will be performed on these characteristics. The number and percentage of participants screened and randomized and the primary reasons for screening failure and discontinuation will be displayed. Demographic variables baseline characteristics, primary and secondary diagnoses, and prior and concomitant therapies will be summarized by treatment either by descriptive statistics or categorical tables.

3.6.5 Japan Safety Run-in Cohort (local Japan protocol version)

For participants from Japan safety run-in cohort, listings of participant demographics, discontinuations, death, adverse events, drug exposure, and efficacy endpoints of OS, PFS, and best response will be provided. An AE summary table will also be provided.

3.7 Interim Analyses

The results of IAs will not be shared with the investigators prior to the completion of the study. Participant-level unblinding will be restricted to an internal unblinded statistician and scientific programmer performing the IA, who will have no other responsibilities associated with the study.

An external DMC will serve as the primary reviewer of the results of the IAs of the study and will make recommendations for discontinuation of the study or protocol modifications to the EOC of the Sponsor (Appendix 1 of the protocol). If the DMC recommends modifications to the design of the protocol or discontinuation of the study, this executive committee (and potentially other limited Sponsor personnel) may be unblinded to results at the treatment level in order to act on these recommendations. The extent to which individuals are unblinded with respect to results of interim analyses will be documented. Additional logistical details will be provided in the DMC Charter.

Treatment-level results from the IA will be provided to the DMC by the unblinded statistician. Prior to final study unblinding, the unblinded statistician will not be involved in any discussions regarding modifications to the protocol, statistical methods, identification of protocol deviations, or data validation efforts after the IA.

Access to the allocation schedule for summaries or analyses for presentation to the eDMC will be restricted to an unblinded internal statistician, and as needed, an internal scientific programmer performing the analysis, who will have no other responsibilities associated with the study.

3.7.1 Efficacy Interim Analyses

Two IAs are planned in addition to the FA for this study. For the IAs and FAs, all randomized participants will be included. Results of the IAs will be reviewed by the DMC. Details of the boundaries for establishing statistical significance with regard to efficacy are discussed further in Section 3.8.

The analyses planned, endpoints evaluated, and drivers of timing are summarized in Table 8.

Analyses	Key Endpoints	Timing	Estimated Time after First Participant Randomized	Primary Purpose of Analysis
IA1	PFS OS ORR	Enrollment is complete with approximately ~7 months of follow-up and ~563 PFS events have been observed.	~29 months	 Interim PFS analysis Interim OS analysis Final ORR analysis
IA2	OS PFS	~410 deaths have occurred and ~17 months after last participant randomized.	~39 months	Interim OS analysisFinal PFS analysis
FA	OS	~483 deaths have occurred and ~27 months after last participant randomized.	~49 months	• Final OS analysis

Table 8 Summary of Interim and Final Analyses Strategy

Abbreviations: FA = final analysis; IA1 = interim analysis 1; IA2 = interim analysis 2; ORR = objective response rate; OS = overall survival; PFS = progression-free survival

Note: If the PFS events accrue slower than expected when participants have been followed up for approximately 7 months, IA1 can take place when at least ~525 PFS events have occurred.

Note: If the OS events accrue slower than expected for IA2 and/or FA, the Sponsor may conduct the analysis with up to additional 3 months of follow-up, or the specified number of events is observed, whichever occurs first.

If an efficacy boundary is crossed at any interim analysis or FA for either PFS or OS, the study will be declared to have met its primary objective.

3.7.2 Safety Interim Analyses

The DMC will be responsible for periodic interim safety reviews, as specified in the DMC charter. Interim safety analyses will also be performed at the time of interim efficacy analyses. Details will be specified in the DMC charter.

3.8 Multiplicity

The study uses the graphical method of Maurer and Bretz [2] to control multiplicity for multiple hypotheses as well as IAs. According to this approach, study hypotheses may be tested more than once, and when a particular null hypothesis is rejected, the α allocated to that hypothesis can be reallocated to other hypothesis tests. Figure 1 shows the initial 1-sided α allocation for each hypothesis in the ellipse representing the hypothesis. The weights for reallocation from each hypothesis to the others are shown in the boxes on the lines connecting hypotheses.

Initial α assigned to OS, PFS and ORR will be 0.019, 0.005 and 0.001, respectively. If any hypothesis is rejected, α will be reallocated to the other hypotheses.

[figure not shown]

Figure 1 Multiplicity Diagram for Type I Error Control (One-Sided)

3.8.1 Objective Response Rate

The primary test of the ORR hypothesis will occur at IA1, at an initial one-sided α level of 0.001. The testing of ORR will be based on all randomized participants in the study. If ORR null hypothesis is not rejected at IA1 at the initially allocated alpha level and if the null hypotheses for OS and PFS are rejected at any analysis time, the p-value from the ORR test at IA1 analysis will be compared to an updated α -level of 0.025.

Based on all randomized participants, the power at α =0.001 as well as the approximate treatment difference required to reach the bound (Δ ORR) are shown in Table 9, assuming underlying 5% and 20% response rates in the control and experimental groups, respectively.

Table 9	Possible α Levels and Approximate Objective Response Rate Difference
Required to	Demonstrate Efficacy for Objective Response at Interim Analysis

α	~Δ Objective Response Rate (ORR)	Power (AORR=0.15)
0.001	0.073	99.9%
0.025	0.047	>99.9%

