3.6.1.3 Objective Response Rate (ORR)

The stratified Miettinen and Nurminen's method will be used for comparison of the ORR between 2 treatment groups. The difference in ORR and its 95% confidence interval from the stratified Miettinen and Nurminen's method with strata weighting by sample size will be reported. The stratification factors used for randomization (See Section 6.3.2 of the protocol) will be applied to the analysis. A sensitivity analysis will be performed for the comparison of ORR based on investigator's assessment.

The point estimate of ORR will be provided by treatment group, together with 95% CI using exact binomial method proposed by Clopper and Pearson (1934).

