3.9 Sample Size and Power Calculations

The study will randomize approximately 736 participants in a 1:1 ratio to the MK-6482 and everolimus arms. PFS and OS are primary endpoints for the study, with ORR as the key secondary endpoint.

Based on all randomized participants, the power of the ORR testing at the allocated α =0.001 is approximately 99.9% to detect a 15-percentage point difference between an underlying 5% response rate in the control arm and a 20% response rate in the experimental arm.

For the PFS endpoint, based on an expected number of 626 events at the final analysis and one interim analysis at 90% of the final target number of events, the study has approximately 96.9% power to demonstrate an HR of 0.7 at an overall α level of 0.005 (1 sided), 99.3% power at an α level of 0.024 (1-sided), and 99.3% power at an α level of 0.025 (1-sided).

For the OS endpoint, based on a target number of 483 events at the final analysis and 2 interim analyses at approximately 62% and 85% of the final target number of events, the study has approximately 85.4% power to detect an HR of 0.75 at an overall α level of 0.019 (1-sided), 85.8% power at an α level of 0.020 (1-sided), 87.4% power at an α level of 0.024 (1-sided), and 87.7% power at an α level of 0.025 (1-sided).

The above sample size and power calculations for PFS and OS assume the following:

• PFS follows an exponential distribution with a median of 4.4 months for the control group NCT01668784 study (nivolumab versus everolimus in advanced RCC).

• OS follows an exponential distribution with a median of 20.0 months for the control group NCT01668784 study (nivolumab versus everolimus in advanced RCC).

- Enrollment period of 22 months
- An annual dropout rate of 20% and \sim 1% for PFS and OS, respectively

• A follow-up period of 17 and 27 months for PFS and OS, respectively, after the last participant enrolls.

The sample size and power calculations were performed using R ("gsDesign" package) and EAST 6.4.

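### Are the ORR differences in SAP Table 9 (0.073 and 0.047) wrong as thresholds for significance?

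*SAP*

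**What the plan says.** SAP section 3.8.1 sets the ORR test: "The primary test of the ORR hypothesis will occur at IA1, at an initial one-sided α level of 0.001". If that test does not reject, and both OS and PFS are later rejected, "the p-value from the ORR test at IA1 analysis will be compared to an updated α -level of 0.025". At either level the decision is therefore a p-value against α.

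The section then introduces Table 9, which shows power together with "the approximate treatment difference required to reach the bound". The same sentence gives the basis: "assuming underlying 5% and 20% response rates in the control and experimental groups, respectively". The table's title begins "Possible α Levels and Approximate Objective Response Rate Difference", and the column header carries a tilde. The entries are 0.073 with power 99.9% at α = 0.001, and 0.047 with power above 99.9% at α = 0.025.

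The test is fixed in SAP section 3.6.1.3: "The stratified Miettinen and Nurminen's method will be used for comparison of the ORR between 2 treatment groups". The size comes from SAP section 3.9: "The study will randomize approximately 736 participants in a 1:1 ratio to the MK-6482 and everolimus arms", that is, 368 per arm.

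**The concern.** The column reads as the smallest observed difference that gives significance. Checked against the planned type of test at the SAP's own control rate, the entries are too large. Observed rates of 5% and 12.3% (difference 0.073) give a one-sided p of about 0.0002, well inside 0.001. Rates of 5% and 9.7% (difference 0.047) give about 0.007, well inside 0.025.

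Tables 10 and 11 sharpen the impression. Their rows for the HR at the bound are described in nearly the same terms, and they are solved at the bound. Table 9 looks as though it was built differently without saying so.

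If a reader used the column as a threshold, a significant ORR result could appear to fall short of a figure printed in the SAP.

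**Working it through.** **Inputs.** n = 368 per arm (736 randomised 1:1, SAP section 3.9). Rates of 5% and 20%, and one-sided α of 0.001 and 0.025 (SAP section 3.8.1). Hence z = 3.0902 and 1.9600. The documents give no response rates by stratum, so the stratified bound cannot be computed; the unstratified Miettinen-Nurminen test stands in for it.

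**Reproducing Table 9.** The unpooled standard error at the design alternative is

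SE = sqrt((0.05 × 0.95 + 0.20 × 0.80)/368) = 0.02375.

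- α = 0.001: 3.0902 × 0.02375 = 0.0734 (stated 0.073)
- α = 0.025: 1.9600 × 0.02375 = 0.0465 (stated 0.047)

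The pooled standard error at the 12.5% midpoint gives 0.0753 and 0.0478, which do not match, so the unpooled formula is the one used. Exact binomial power at 5% versus 20% and α = 0.001 is 0.9996, in line with the stated 99.9%.

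**Solving at the bound.** Let d be the difference and p̄ the mean of the two observed rates. Solve

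d = z × sqrt(2 × p̄ × (1 − p̄)/368 × 736/735).

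| What is held fixed | α = 0.001 | α = 0.025 |
|---|---|---|
| Control 3% | 0.053 | 0.030 |
| Control 5% | 0.0622 | 0.0365 |
| Control 7% | 0.070 | 0.042 |
| Control 10% | 0.079 | 0.048 |
| Experimental 20% | 0.083 | 0.055 |
| Table 9 | 0.073 | 0.047 |

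The control 5% value at α = 0.025 is 0.03646, so 0.036 to three decimals. Relative to the control 5% row, Table 9 is high by 0.073 − 0.062 = 0.011 and 0.047 − 0.036 = 0.011, about 1 percentage point each. The stated values are exact at an observed control rate of about 7.9% (for 0.073) and 9.7% (for 0.047).

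**In whole responders, near a 5% control rate:**

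- α = 0.001: 18 versus 41 (difference 0.0625, p = 0.0009; 18 versus 40 gives p = 0.0013), or 19 versus 43 (0.0652).
- α = 0.025: 18 versus 32 (0.0380, p = 0.020; 18 versus 31 gives p = 0.027), or 19 versus 33 (0.0380).

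**Tables 10 and 11.** The HR at the bound is exp(−2z/sqrt(events)). PFS at IA1: z = 2.7383 with 563 events gives 0.7939 (stated 0.7938). OS at the final analysis: z = 2.1541 with 483 events gives 0.8220 (stated 0.8220). The variance here depends only on the event count, so no response rate has to be assumed.

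**How often the gap would show.** The event of interest is a rejection at α = 0.001 with an observed difference below 0.073. Under the planned 5% versus 20% its exact probability is about 0.01%. Under a true 5% versus 11%, a scenario not in the documents and assumed here for illustration, it is about 20%.

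**The case for a change.** The best case for a correction is that the label and the calculation disagree. A difference required to reach the bound should be computed at the bound, where rates of 5% and 20% cannot both be observed. The gap is more than rounding: 0.011/0.062 is about 18% of the required difference at α = 0.001, and 0.011/0.036 is about 30% at α = 0.025. At a 5% control rate it always runs upward. The HR columns are also called approximate, yet they agree with their formula to within about 0.0002 in the cells checked. The repair would cost two numbers and a footnote.

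The diagnosis stands: the column uses the variance at the design alternative. The conclusion that the table is in error does not. Both entries follow from the rates that the sentence names. For a binary endpoint the critical difference depends on the observed rates, so any single figure is a convention. Fixing the control rate at 5% is a natural convention, but the text gives underlying rates for both arms and does not mention an observed control rate. Fixing the experimental rate at 20% instead would put Table 9 too low, and its entries lie between the two solutions. Replacement figures would again be unstratified approximations to a stratified test. The contrast with Tables 10 and 11 is weak as well, because the log-rank calculation has no nuisance rate to choose.

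**Conclusion.** No change to the plan is needed. Table 9 gives a labelled approximation, taken at the design rates, that differs by about 1 percentage point from the value solved at an observed control ORR of 5% (about 0.062 and 0.036 against 0.073 and 0.047). Nothing operates on the column. The ORR hypothesis is decided by the p-value of the stratified test against 0.001 or 0.025, so the type I error, power, sample size and any claim would be the same whichever figures were printed. Under the planned effect, a significant result below the printed 0.073 would almost never occur (about 0.01%). A statistician who wants the threshold for the observed control rate can compute it in one line. A note giving the formula would be an editorial courtesy and no more.

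This rests on 368 per arm and on the unstratified test as a stand-in for the stratified one. Stratification could move the solved values, by an amount the documents do not allow to be calculated. It would not alter the p-value rule.

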3.8.2 Progression-free Survival

The initial α -level for testing the PFS hypothesis is 0.005. If the null hypothesis for OS is rejected, Figure 1 shows that α =0.019 from the OS hypothesis is almost fully reallocated to PFS hypothesis testing. Thus, the PFS null hypothesis may be tested at α =0.005 (initially allocated α), α =0.024 if the OS hypothesis is rejected and the ORR hypothesis is not rejected, or at α =0.025 if both the OS and ORR null hypotheses are rejected. Table 10 shows the boundary properties for each of these α levels for the PFS analysis. Note that the final row indicates the total power to reject the null hypothesis for PFS at each α level. A Lan-DeMets O'Brien-Fleming spending function was used to derive the bounds and boundary properties of the PFS hypothesis at each analysis based on the estimated number of events.

Since the timing of the PFS interim analysis at IA1 will be dependent on both the number of PFS events and a minimum follow-up time, for the PFS hypothesis, alpha will be spent as a function of the minimum of the actual event information fraction and the expected event information fraction at IA1. If events accrue faster than expected, this approach ensures that the actual spending will be no more aggressive than the planned, while at the same time ensuring that not all alpha is spent prior to the accrual of the final planned event counts.

The expected number of events at the final PFS analysis is \sim 626. The final PFS analysis at IA2 will use the remaining Type I error not spent at the IA1, regardless of the actual number of PFS events observed. The p-value bound at the final PFS analysis will be calculated by considering the correlation between the test statistics as determined by the actual number of PFS events at IA1 and the final PFS analysis at IA2.

Table 10 summarizes the boundary properties of 3 possible scenarios.

Analysis	Value	α=0.005	α=0.024	α=0.025
IA1: 90%*	Ζ	2.7383	2.1119	2.0937
N = 736	p (1-sided) ^a	0.0031	0.0173	0.0181
Events: 563 Month: 29	HR at bound ^b	0.7938	0.8369	0.8382
Wohth. 29	P(Cross) if HR=1°	0.0031	0.0173	0.0181
	P(Cross) if HR=0.7 ^d	0.9330	0.9831	0.9839
IA2:100%	Ζ	2.6421	2.0694	2.0529
N = 736	p (1-sided) ^a	0.0041	0.0193	0.0200
Events: 626 Month: 39	HR at bound ^b	0.8095	0.8474	0.8486
Wolten. 39	P(Cross) if HR=1 ^c	0.0050	0.0240	0.0250
	P(Cross) if HR=0.7 ^d	0.9685	0.9928	0.9931

Table 10Efficacy Boundaries and Properties for Progression-Free SurvivalAnalyses

Abbreviations: HR = hazard ratio; IA = interim analysis; OS = overall survival; PFS = progression-free survival

The number of events and timings are estimated approximately.

*Percentage of the target number of events at PFS final analysis anticipated at IA.

^ap (1-sided) is the nominal α for testing.

^bHR at bound is the approximate HR required to reach an efficacy bound.

^cP (Cross if HR=1) is the probability of crossing a bound under the null hypothesis.

^dP(Cross if HR=0.7) is the probability of crossing a bound under the alternative hypothesis.

Note that if the α -reallocation from OS hypothesis testing occurs at an analysis after hypothesis testing for PFS has been completed, the previously computed PFS test statistic for the PFS final analysis may be re-evaluated based on the updated bounds.

